5.2.1.3.3. Previous therapies for colorectal cancer

The existence of a previous drug treatment (Yes, No) is defined from the presence, or not of an “anatomical therapeutic chemical classification” and/or a “preferred name” for the previous drug treatment at inclusion visit.

The existence of a previous metastatic drug treatment (Yes, No) is defined from the presence, or not of an “anatomical therapeutic chemical classification” and/or a “preferred name” for the previous drug treatment after the date of 1st metastasis.

The existence of a previous adjuvant drug treatment (Yes, No) is defined from the presence or not of a previous drug treatment with an adjuvant indication.

The existence of a previous neoadjuvant drug treatment (Yes, No) is defined from the presence or not of a previous drug treatment with a neoadjuvant indication.

The existence of a previous fluoropyrimidine drug treatment (Yes, No) is defined from the presence, or not of a previous drug treatment belonging to the list 3678.0.

The existence of a previous irinotecan drug treatment (Yes, No) is defined from the presence, or not of a previous drug treatment belonging to the list 3674.0.

The existence of a previous oxaliplatin drug treatment (Yes, No) is defined from the presence, or not of a previous drug treatment belonging to the list 3675.0.

The existence of a previous anti-VEGF monoclonal antibody drug treatment (Yes, No) is defined from the presence, or not of a previous drug treatment belonging to the list 4281.0.

The existence of a previous anti-EGFR monoclonal antibody drug treatment (Yes, No) is defined from the presence, or not of a previous drug treatment belonging to the list 4280.0.

Number of prior regimens for mCRC is calculated as the sum of previous drug treatments for mCRC except if reported in a maintenance indication.

The duration of previous metastatic regimen containing anti-EGFR monoclonal Anti Body (months) is defined as (last previous anti-EGFR monoclonal Anti Body drug treatment end date – first previous anti-EGFR monoclonal Anti Body drug treatment start date)/30.44.

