2. BACKGROUND INFORMATION

2.1. Metastatic Colorectal Cancer

Colorectal cancer (CRC) is the third most common cancer type in the world in terms of incidence and the second one in terms of mortality, with an estimated 1,800,000 new cases and 881,000 deaths in 2018.¹

Approximately 25% of patients present with metastases at initial diagnosis and approximately 50% of patients with early-stage disease will develop metastases, which contribute to the high mortality rates reported for CRC²

Therapy for patients with metastatic CRC (mCRC) has mostly palliative intention, except for patients with limited metastatic disease in the liver for whom a surgical approach with curative intent may be used. Systemic therapy for mCRC typically pairs a chemotherapy backbone regimen with a biologic agent. Oxaliplatin, irinotecan and 5-fluorouracil commonly form the chemotherapy backbone in various regimens of two-drug or three-drug regimens. A biologic agent such as anti-vascular endothelial cell growth factor (VEGF) or anti-epidermal growth factor receptor (EGFR) antibody is added to the chemotherapy regimen depending on tumour-specific and patient-specific factors. Molecular testing of the tumour is required before considering treatment with anti-EGFR antibodies such as cetuximab and panitumumab. Mutations in hot spot regions of **CCI** of KRAS or of NRAS genes (occurring in approximately 55% of mCRC patients) and the BRAF-**CCI** (occurring in approximately 5-15% of mCRC patients) have been associated with lack of benefit from anti-EGFR treatment.³⁻⁵ Additionally, “sidedness” of the tumour has a key role in the metastatic setting and is increasingly recognised as a predictive marker of response to anti-EGFR drugs, with left sided tumours demonstrating better outcome.²

Participants with mCRC typically receive several lines of therapy. In clinical practice, of all mCRC patients receiving first-line chemotherapy, approximately 50% go on to receive second line chemotherapy, and of these patients, approximately 25% go on to receive third-line chemotherapy.⁶ This “continuum of treatment” with several subsequent lines of therapy has led to an improvement of the clinical outcome for patients with mCRC, in the last decade. Today, the median overall survival (OS) for patients with mCRC is approximately 30 months; more than double that of 20 years ago⁷

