5.1.2. Medical and therapeutic criteria

2. Participants must have histologically or cytologically confirmed adenocarcinoma of mCRC (all other histological types are excluded), not amenable to surgical intervention due to either medical contraindications or non-resectability of the tumour.
3. Based on ctDNA screening blood test analysis participants should be:
 - Without RAS (KRAS and NRAS) mutations in any of the following codons:
 - CCI [REDACTED]
 - CCI [REDACTED]
 - CCI [REDACTED]
 - Without BRAF CCI [REDACTED].
4. Participants must have measurable or non-measurable lesion according to RECIST v1.1.

5b. Participants must have received at least 2 prior regimens of standard chemotherapy for mCRC and had demonstrated progressive disease or intolerance to their last regimen. The following characteristics apply:

- Prior standard chemotherapy must not have included trifluridine/tipiracil but must have included all of the following agents approved and available in each country:
 - Fluoropyrimidines, irinotecan and oxaliplatin.
 - At least one anti-VEGF pathway inhibitor (bevacizumab and/or aflibercept and/or ramucirumab and/or regorafenib).
 - At least one anti-EGFR mAb (cetuximab or panitumumab).
 - Patients with known MSI-H/dMMR tumours are eligible if they have received previous treatment with immune checkpoint inhibitors according to approved indication.
- Participants must have progressed during or within 6 months of the last administration of the last standard chemotherapy regimen. Participants who have withdrawn from standard treatment due to unacceptable toxicity warranting discontinuation of treatment and precluding retreatment with the same agent prior to progression of disease will be eligible to enter the study.
- Participants who received adjuvant/neoadjuvant chemotherapy and had recurrence during or within 6 months of completion of the adjuvant/neoadjuvant chemotherapy are permitted to count the adjuvant/neoadjuvant therapy as one regimen of chemotherapy.

6a Participants should have received previous treatment with commercially available anti-EGFR mAbs for ≥ 16 weeks.

7. Ability to swallow oral medication.

8a. Estimated life expectancy ≥ 12 weeks. This criterion should be rechecked at inclusion visit (Safety Lead-in part) or randomisation visit.

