3.2.4.5. Previous therapies related to colorectal cancer

All previous therapies for the colorectal cancer will be summarized according to the following variables for patients in the SS:

- Previous neo-adjuvant drug treatment (Yes, No).
- Previous adjuvant drug treatment (Yes, No).
- Previous adjuvant and neo-adjuvant drug treatment (Yes, No).
- Previous adjuvant or neo-adjuvant drug treatment (Yes, No).
- Previous metastatic drug treatment (Yes, No).
- Previous adjuvant or neo-adjuvant fluoropyrimidine (Yes, No).
- Previous metastatic fluoropyrimidine (Yes, No).
- Previous metastatic irinotecan (Yes, No).
- Previous adjuvant or neo-adjuvant oxaliplatin (Yes, No).
- Previous metastatic oxaliplatin (Yes, No).
- Previous metastatic anti-VEGF monoclonal Anti Body (Yes, No).
- Previous neo-adjuvant anti-EGFR monoclonal Anti Body (Yes, No) in RAS wild type patients only as documented in the e-CRF.
- Previous metastatic anti-EGFR monoclonal Anti Body (Yes, No).
- Response to previous metastatic regimen containing anti-EGFR monoclonal Anti Body (CR, PR, SD).
- Skin toxicity with previous metastatic regimen containing anti-EGFR monoclonal Anti Body (Yes, No).
- Skin toxicity with previous metastatic regimen containing anti-EGFR monoclonal Anti Body (Grade 1-2, Grade 3-4, No skin toxicity).
- Duration of previous metastatic regimen containing anti-EGFR monoclonal Anti Body.
- Number of prior regimens for mCRC.
- Number of prior adjuvant or neoadjuvant regimens.
- Reason for treatment discontinuation of the last regimen prior to randomisation (Toxicity, Progressive disease, Other).
- Last regimen prior to randomisation containing anti-EGFR monoclonal Anti Body (Yes, No).

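### SAP 5.2.1.3.3 derives the number of prior metastatic regimens by adding up drugs, so two treatment lines would be reported as about 3 to 8 if the e-CRF records are per drug

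*SAP*

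**What the plan says.** SAP 3.2.4.5 lists "Number of prior regimens for mCRC" among the prior-therapy variables summarised in the Safety Set, with no categories attached. SAP 5.2.1.3.3 derives it: "Number of prior regimens for mCRC is calculated as the sum of previous drug treatments for mCRC except if reported in a maintenance indication". The section has no step that groups drugs given together.

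The same section shows what it means by a drug treatment. One exists if an ATC class and/or preferred name is present "for the previous drug treatment at inclusion visit". Drug classes are then flagged one at a time. Prior irinotecan, for example, "is defined from the presence, or not of a previous drug treatment belonging to the list 3674.0". Fluoropyrimidine, oxaliplatin, anti-VEGF antibody and anti-EGFR antibody each have a list of their own. The anti-EGFR drug treatment also has its own start and end dates, which give the duration variable.

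The protocol uses the word regimen for a combination. Section 2.1 says "Oxaliplatin, irinotecan and 5-fluorouracil commonly form the chemotherapy backbone in various regimens of two-drug or three-drug regimens" and "Systemic therapy for mCRC typically pairs a chemotherapy backbone regimen with a biologic agent". Criterion 5b in Section 5.1.2 asks for at least two prior regimens, which must cover a fluoropyrimidine, irinotecan, oxaliplatin, an anti-VEGF pathway inhibitor and an anti-EGFR antibody, as far as these are approved and available in the country.

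**The concern.** The label says regimens, but the derivation sums something the section defines at drug level. Two lines of combination therapy, which is the ordinary history in this population, would not come out as 2. Because criterion 5b calls for five kinds of agent, almost every participant will have had at least one combination line, so the error would run in one direction and affect nearly all of them.

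At stake is the description of the population. A reader who judges toxicity or best overall response in about 25 participants will look at the number of prior regimens to see how heavily pre-treated they were. A median of, say, 6 would suggest a much later-line group than the third-line or later setting described in Protocol Section 2.4.

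**Working it through.** The documents state no result for this variable, so there is no figure to reproduce. No sample size, error rate or event count depends on it. The check is a direct count.

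**Inputs**
- Counting rule: SAP 5.2.1.3.3, sum of non-maintenance drug treatments for metastatic disease.
- Drugs in a backbone: 2 or 3 (Protocol 2.1).
- Biologics per combination line: 1 (Protocol 2.1).
- Minimum prior regimens: 2 (Protocol 5.1.2, criterion 5b).
- Assumption: one e-CRF record per drug.

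**Formula.** Reported count = sum over metastatic, non-maintenance lines of (backbone drugs + biologics). Intended count = number of such lines.

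**Two combination lines**
- Two-drug backbones in both lines: (2 + 1) + (2 + 1) = 6.
- One two-drug and one three-drug backbone: (2 + 1) + (3 + 1) = 7.
- Three-drug backbones in both lines: (3 + 1) + (3 + 1) = 8.

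The intended count is 2 each time.

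**Other histories with two metastatic lines** (illustrative; the compositions are assumptions)

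| History | Records summed | Reported | Lines |
|---|---|---|---|
| Oxaliplatin/fluoropyrimidine + anti-VEGF; then irinotecan/fluoropyrimidine + anti-EGFR | 3 + 3 | 6 | 2 |
| Three-drug backbone + anti-VEGF; then irinotecan + anti-EGFR | 4 + 2 | 6 | 2 |
| Three-drug backbone + anti-VEGF; then anti-EGFR alone | 4 + 1 | 5 | 2 |
| Adjuvant oxaliplatin/fluoropyrimidine (not summed); irinotecan/fluoropyrimidine + anti-VEGF; then anti-EGFR alone | 3 + 1 | 4 | 2 |
| Adjuvant oxaliplatin/fluoropyrimidine (not summed); irinotecan + anti-VEGF; then anti-EGFR alone | 2 + 1 | 3 | 2 |

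The range is therefore 3 to 8 against 2. A three-line history (oxaliplatin/fluoropyrimidine + anti-EGFR; irinotecan/fluoropyrimidine + anti-VEGF; regorafenib) gives 3 + 3 + 1 = 7 against 3.

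**If the assumption fails.** With one e-CRF record per combination, two lines give two records, and the rule returns 2.

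**The case against.** The strongest reply is that the e-CRF is not in the documents. The list look-ups ask only whether a prior treatment belongs to a list; they do not say that one record is one agent. SAP 3.2.4.5 speaks of a regimen containing an anti-EGFR antibody and of the last regimen, and SAP 5.2.1.3.2 refers to progression during the last regimen, so some regimen-level capture may exist. If a record is a whole combination, nothing is wrong with the number. This stands as a condition on the size of the error. It does not rescue the text: the section identifies drug treatments by drug, gives no grouping rule, and elsewhere the SAP treats a drug and the regimen containing it as different things.

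The second reply concerns consequences, and it largely stands. A reader might infer that the rule disturbs the stratification factor of 2 versus 3 or more regimens, or pushes nearly everyone into the upper class. The documents do not support this. The randomised part is cancelled (SAP 1 and 1.2.2), the current SAP has no such class, and subgroups are not applicable (SAP 2.3). Nor does the variable decide eligibility. Criterion 5b is checked at screening, and breaches are reported as protocol deviations (SAP 3.2.2 and 5.2.1.2).

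A reader might also infer that the count wrongly leaves out adjuvant or neoadjuvant therapy with early recurrence, because participants "are permitted to count the adjuvant/neoadjuvant therapy as one regimen of chemotherapy". That does not follow. The criterion is a permissive entry rule, the variable is labelled as metastatic, and SAP 3.2.4.5 reports adjuvant and neoadjuvant regimens in a separate row. Adding them here would show the same course twice.

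**Conclusion.** The point holds within limits. Read as written, SAP 5.2.1.3.3 counts drugs and calls the result regimens. If e-CRF records are per drug, a participant with two metastatic lines would be reported with about 3 to 8, and with 6 to 8 only when both lines are combinations of the kind Protocol 2.1 describes. It would be too strong to say that every participant is reported with 6 to 8: single-agent lines and agents given only in the adjuvant setting bring the figure down to 3 to 5.

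The damage is to one descriptive baseline row, and to the adjuvant/neoadjuvant regimen count if it is built the same way, since SAP 5.2.1.3.3 gives no separate derivation for that row. The retained analyses (safety with DLTs, and best overall response; SAP 1.1) do not use either count. The individual agent-class rows in SAP 3.2.4.5 are unaffected. The result rests on the per-drug record assumption and on the illustrative line compositions. It is still worth correcting, because a reader has no way to see from the table that the figure is a drug count.

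**What to change.** Redefine the number of prior regimens for metastatic disease as the number of distinct treatment lines, leaving out maintenance. Drugs that share an e-CRF regimen or line identifier count once. If there is no such identifier, group records by overlapping dates and have a medical reviewer confirm the grouping. Use the same grouping for the separate adjuvant/neoadjuvant count, and do not add adjuvant courses to the metastatic count. The SAP should also say whether one prior-treatment record is a drug or a combination; if it is a combination, that sentence alone settles the matter.

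The cost is one reworded derivation, its program, and a short review of about 25 treatment histories. No new data collection should be needed, since Protocol Section 6.3 already has all anticancer therapies for the disease collected from diagnosis onwards.

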4.1.1. Study plan

This is a randomised, open label, multi-centre, two-arm Phase 3 study to evaluate futuximab/modotuximab in combination with trifluridine/tipiracil *versus* trifluridine/tipiracil monotherapy in participants ≥ 18 years of age with KRAS/NRAS and BRAF WT mCRC who were previously treated with chemotherapy (including oxaliplatin, irinotecan and 5-fluorouracil, anti-VEGF agents) and with anti-EGFR mAb therapy for ≥ 16 weeks.

The study will comprise two parts a Safety Lead-In part in approximately 25 participants and a Randomised part in approximately 500 participants.

The study design is depicted in [Figure \(4.1.1\) 1](#).

Figure (4.1.1) 1 - CL3-95026-001 Study Design

AE = adverse event; DLT = dose-limiting toxicity; ECD = extracellular domain; EGFR = epidermal growth factor receptor; mCRC = metastatic colorectal cancer; TEAE = treatment-emergent adverse event; STEAE = serious treatment emergent adverse events

Figure (4.1.1) 2 - Study plan for the Safety Lead-In Part

[figure not shown]
[figure not shown]

Figure (4.1.1) 3 - Study plan for the Randomised part

The study start is defined as the date of the first visit of the first participant.

The study will be divided into the following periods for each participant:

- Screening visit/Screening period (maximum 28 days):
 - Screening visit: after signature of the Informed Consent Form(s) (ICF) to check screening criteria and decide if participant can be screened for the study.
 - Screening period: if the participant is screened in the study, check the inclusion and exclusion criteria and decide if participant can be included in the study.
 - Randomisation: included participants will be randomly assigned to one of the two treatment groups:
 - Arm A: trifluridine/tipiracil + futuximab/modotuximab.
 - Arm B: trifluridine/tipiracil.
- Treatment period: participants will be treated until they meet a discontinuation criterion as described in [Section 5.8.1](#). The participants should receive the first dose of first IMP (Day 1 of Cycle 1) within 3 days after inclusion (in the Safety Lead-in part) or after randomisation.
- Withdrawal visit (WV): should be conducted within approximately 4 weeks following the date of study treatment withdrawal and before the start of a new anticancer therapy.
- Follow-up period: after the WV the participant will be followed every 8 weeks (\pm 10 calendar days):

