OS for each arm will be summarized using Kaplan Meier curves and further characterised in terms of the median and survival probabilities at 6, 12 and 18 months along with the corresponding 2-sided 95% CI for the estimates.

The hazard ratio of OS with its 95% confidence interval will be estimated with a stratified Cox proportional hazard model (stratification factors based on IWRS data).

For missing data (not linked to intercurrent events), *i.e.* participants without documentation of death (lost to follow-up, withdrawal of consent, administrative end of study), the OS will be censored on the last contact date the participant was known to be alive or the cut-off date, whichever is earlier.

Sensitivity analyses

As sensitivity analyses, the following analyses will be done:

- The proportional hazards assumption will be checked. If relevant, other statistical method could be used.
- OS analysis based on PPS.

Other sensitivity analyses will be defined in the SAP if necessary.

Supplementary analyses

Subgroup analyses

OS subgroup analyses are planned to further explore the homogeneity of the treatment effect across participant subsets. Depending on the sample size, the following subgroups will be examined: ECOG PS (0, 1), extracellular domain EGFR mutations (ECD) (presence, absence), previous regimens of treatment (2, \geq 3), region (North America, European Union, Asia, Rest of the World), time since diagnosis of 1st metastasis (< 18, \geq 18 months), location of primary disease (right, left), gender (female, male), age (< 70, \geq 70 years), prior surgical resection (yes, no), number of metastatic sites (1-2, \geq 3), neutrophils to lymphocytes ratio (NLR < 3, NLR \geq 3), neutrophils to lymphocytes ratio (NLR < 5, NLR \geq 5), response to previous treatment with anti-EGFR (CR/PR, SD), last previous regimen (anti-EGFR, no anti-EGFR), previously treated with anti-VEGFs treatment (yes, no), skin toxicity with previous anti-EGFR (yes, no), skin toxicity with previous anti-EGFR (Grade 1-2, Grade 3-4, no toxicity), duration of previous anti-EGFR (< 8, \geq 8 months), Race (White, American Indian/Alaska native, Asian, Black/African

American, Native Hawaiian/Other pacific islander), Premedication with antibiotics for skin toxicity (yes, no).

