1. INTRODUCTION

This Statistical Analysis Plan (SAP) details the planned analyses to be performed for the Safety Lead-In part, in accordance with the main characteristics of the amended clinical study protocol of 16th August 2022.

The randomised part has been cancelled due to study discontinuation during the Safety Lead-in part for strategic reasons. All information concerning the randomised part is described in the protocol.

The templates for Tables, Listings and Graphs (TLG) are described in a separate document.

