Missing end date of the last prior therapy		Substituted end date of the last prior therapy
./mm/yyyy	⇒	end date of the last prior therapy = start date of the last prior therapy + 1day if same month and year otherwise: end date of the last prior therapy = 01/mm/yyyy
./.../yyyy	⇒	end date of the last prior therapy = start date of the last prior therapy + 1day if same year otherwise: end date of the last prior therapy = 01/01/yyyy
./.../...	⇒	end date of the last prior therapy = start date of the last prior therapy + 1day
Missing start date of a previous treatment	⇒	Substituted start date of a previous treatment
./mmm/yyyy	⇒	01/mmm/yyyy
./.../yyyy	⇒	01/JAN/yyyy
./.../....	⇒	Inclusion date

Note:
 ./mm/yyyy = missing day
 ./.../yyyy = missing day and month
 ./.../.... = missing date

RAS status

Table (5.2.1.3.2) 2 - RAS status

KRAS	NRAS	RAS
MUTANT	whatever (mutant, wild, missing)	MUTANT
whatever (mutant, wild, missing)	MUTANT	MUTANT
WILD	WILD	WILD
MISSING	WILD	NE
WILD	MISSING	NE
MISSING	MISSING	NE

Stage at diagnosis

Table (5.2.1.3.2) 3 - Staging based on classification

Stage in classes	AJCC stage	Dukes' classification	Astler-Coller modified Dukes' classification
	Stage 0	-	-
I-II	Stage I	A	A
I-II	Stage I	A	B1
I-II	Stage II-A	B	B2
I-II	Stage II-B	B	B2
I-II	Stage II-C	B	B3

III	Stage III-A	C	C1
	Stage III-B	C	C2
		C	C1/C2
		C	C1
	Stage III-C	C	C2
		C	C2/C3
		C	C3
IV	Stage IV-A		D
	Stage IV-B		
	Stage IV-C		

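### SAP 5.2.1.3.3 reports the span from first anti-EGFR start to last anti-EGFR end as a treatment duration, so gaps between courses count and a wholly missing start date can give a negative value

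*SAP*

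**What the plan says.** SAP 3.2.4.5 lists "Duration of previous metastatic regimen containing anti-EGFR monoclonal Anti Body" among the prior-therapy descriptors for the Safety Set, with no cut-point or classes. SAP 5.2.1.3.3 derives it in months as "last previous anti-EGFR monoclonal Anti Body drug treatment end date – first previous anti-EGFR monoclonal Anti Body drug treatment start date)/30.44". Nothing is subtracted for time between courses. The two date terms refer to any earlier anti-EGFR antibody, while the label refers to the metastatic setting. SAP 3.2.4.5 lists neo-adjuvant and metastatic anti-EGFR treatment as separate items.

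Table (5.2.1.3.2) 1 in the SAP has a row block headed "Missing start date of a previous treatment". A missing day becomes the first of the month, and a missing day and month becomes 1 January. A wholly missing date becomes the inclusion date.

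SAP 5.1.3 adds one day to durations unless a definition says otherwise; this formula does not add it.

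Two protocol items concern the same quantity. Screening criterion 6a (Protocol 5.1.2) reads "Participants should have received previous treatment with commercially available anti-EGFR mAbs for ≥ 16 weeks". The overall-survival subgroup list in Protocol 10.1.2.4.2.1 includes "duration of previous anti-EGFR (< 8" months against 8 months or more.

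**The concern.** A reader of the baseline table will take a line labelled as the duration of an anti-EGFR regimen to mean time on anti-EGFR treatment. The formula gives that only for one continuous course. With two or more courses, the time between them, spent off treatment or on other drugs, is reported as anti-EGFR duration.

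The entry criteria leave room for this. Criterion 5b asks for at least one anti-EGFR antibody, criterion 6a uses the plural, and no criterion limits a patient to a single course. A patient treated in both the neo-adjuvant and the metastatic setting would have the whole interval from the first start to the last end reported under a metastatic label.

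The missing-date rule adds a second fault. It can place the start of a previous treatment after its end.

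What is at stake is one descriptive line. It is, however, the only SAP statistic that quantifies earlier anti-EGFR duration, and that duration is part of how the protocol defines its population. SAP 3.1 summarises quantitative data by mean, median, quartiles, minimum and maximum, so in a small single-arm group a few affected values are visible.

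**Working it through.** The plan states no figure that can be reproduced, so the check applies its formula to example histories. Course lengths and gaps are assumptions; neither document gives any.

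**Inputs**
- 30.44 days per month (SAP 5.1.3 and the formula itself).
- Four weeks (28 days) without anticancer therapy before inclusion (Protocol 5.2.1, criterion 14a).
- About 25 planned lead-in participants, with a review at 12 (SAP 1.3).

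**Separated courses**

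SAP value = (course 1 + gap + course 2)/30.44. Time on treatment = (course 1 + course 2)/30.44. The difference is gap/30.44.

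| Assumed history | SAP value (months) | On treatment (months) | Difference (months) |
|---|---|---|---|
| 20 weeks, single course | 140/30.44 = 4.60 | 140/30.44 = 4.60 | 0 |
| 24 weeks, 4-week gap, 8 weeks | 252/30.44 = 8.28 | 224/30.44 = 7.36 | 28/30.44 = 0.92 |
| 20 weeks, 26-week gap, 12 weeks | 406/30.44 = 13.34 | 224/30.44 = 7.36 | 182/30.44 = 5.98 |
| 16 weeks, 365-day gap, 8 weeks | 533/30.44 = 17.51 | 168/30.44 = 5.52 | 365/30.44 = 11.99 |

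In every row the first course alone reaches 16 weeks, so each patient meets criterion 6a whether it is read as continuous or cumulative. The table ignores the one-day convention, which is worth 1/30.44 = 0.03 month per course.

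**Effect on the summary**

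One patient with a 365-day gap raises the mean by 11.99/25 = 0.48 month among 25 participants, or by 11.99/12 = 1.00 month among 12. The same patient may also set the maximum.

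**Wholly missing start date, single course**
1. The substituted start is the inclusion date.
2. Under criterion 14a the end date is at least 28 days before inclusion.
3. The SAP value is (end - inclusion)/30.44, which is at most -28/30.44 = -0.92 month. It becomes more negative the earlier the course ended.

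If another anti-EGFR course has a known start, that date is taken as the first start and the value is positive.

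**The case against.** The best defence is that the SAP states its definition openly and anyone can reproduce it. The variable is one of roughly 20 prior-therapy descriptors and feeds no endpoint, test or decision. The re-challenge trial in Protocol 2.3.2 is a different study, and neither document shows that any patient here had two courses. The negative value needs a patient whose only anti-EGFR course, or every course, lacks a start date altogether.

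Most of this stands and limits the size of the point. It does not remove it. An openly stated formula can still fail to measure what its label says, and a rule that can return a negative duration needs correcting however rarely it applies.

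A reader might go further and infer that patients are placed on the wrong side of the 16-week criterion or the 8-month subgroup cut. The documents do not support that:
- **16 weeks.** Eligibility is settled at the screening visit, whose purpose is "to check screening criteria and decide if participant can be screened for the study" (Protocol 4.1.1). Nothing ties the SAP variable to that decision, and unmet entry criteria are reported as protocol deviations (SAP 3.2.2 and 5.2.1.2). The protocol's per-protocol set used this criterion, but it is a subset of randomised participants and is not in SAP version 2.0.
- **8 months.** The split is an overall-survival subgroup and a Cox covariate for the Randomised part. SAP section 1 records that "The randomised part has been cancelled due to study discontinuation during the Safety Lead-in part for strategic reasons", and SAP 2.3 marks subgroups as not applicable.

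**Conclusion.** The point holds as a minor, descriptive fault. SAP 5.2.1.3.3 reports elapsed span under a treatment-duration label and does not restrict its dates to the metastatic setting as the label does. Under the SAP's own substitution rule it can also return an impossible value.

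The error is zero for a single dated course and equals the gap otherwise, from 0.92 to 11.99 months in the two-course examples above. It is -0.92 month or lower as a reported value when the sole start date is wholly missing.

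These sizes rest on assumed histories. The number of patients with several courses or with no start date is not stated, so it cannot be said that the actual table is inflated, only that it can be. No planned analysis in SAP version 2.0 classifies anyone with this variable. The 8-month split would be affected only if the same derivation were reused for it.

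**What to change.** In SAP 5.2.1.3.3, define the duration as the sum of (end date - start date + 1)/30.44 over anti-EGFR-containing regimens given in the metastatic setting, merging overlapping periods. This uses the metastatic definition already in that section and the one-day convention of SAP 5.1.3.

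For this variable, do not apply the inclusion-date substitution. Leave the duration missing when a start date is wholly missing. The existing rules for partly missing dates can stay.

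The least that would do is to relabel the line as time from first start to last end of anti-EGFR therapy. That cures the wording but not the negative values.

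The cost is slightly more programming, with no new data, since the current formula already draws on treatment start and end dates. Some reported durations become shorter and a few may become missing.
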